## **Time to Inhibitor Development**

The cumulative incidence of inhibitors over time (EDs) will be estimated using the Kaplan-Meier method. For patients who do not have an inhibitor, follow-up time will be censored at the last ED at the time of analysis. This will be presented graphically for high and low titer (CS and NCS) inhibitors and overall, if at least 5 patients develop positive inhibitor.

Additionally a summary of EDs at time of inhibitor development will be provided, again for high and low titer (CS and NCS) inhibitors and overall. This will include Kaplan-Meier estimates of cumulative incidence of inhibitor development at 10, 20 and 50 EDs.

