**High and Low Titer Positive Inhibitors**

A positive inhibitor test result is defined as an inhibitor test result of  $\geq 0.60$  BU/mL that is confirmed by a second test result of  $\geq 0.60$  BU/mL from a separate sample, drawn 2 to 4 weeks following the original sample. Both tests must be performed by the central laboratory using the Nijmegen-modified Bethesda assay. The date of the inhibitor is the date of the sample with the first positive test result which was subsequently confirmed.

- A positive low titer inhibitor is defined as an inhibitor test and confirmatory test, both with results of  $\geq 0.60$  and  $< 5.00$  BU/mL.
- A positive high titer inhibitor is defined as an inhibitor test and confirmatory test, both with results of  $\geq 5.00$  BU/mL.

Patients with discordant inhibitor test results (initial low titer result followed by high titer result or initial high titer result followed by low titer result) should have repeat inhibitor testing performed by the central laboratory from a third separate sample, drawn 2 to 4 weeks following the previous sample.

- If 2 of 3 test results are  $< 5.00$  BU/mL, the inhibitor is considered low titer.
- If 2 of 3 test results are  $\geq 5.00$  BU/mL, the inhibitor is considered high titer.

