## Inhibitor Subgroups

Patients developing a positive inhibitor after exposure to rFIXFc will be included in Inhibitor Subgroup. Within this subgroup, there are several further classifications:

1. Patients with high-titer inhibitors, defined as in Section 5.2.4
2. Patients with low-titer inhibitors, defined as Section 5.2.4, that meet the below clinically meaningful criteria
3. Patients with low-titer inhibitors that do not meet the below clinically meaningful criteria

The delineation of clinically meaningful will be performed on a case-by-case basis via medical adjudication prior to the final analyses, based upon the data available for the analysis. This assessment will take account of relevant clinical factors, including but not limited to:

- Entry to the ITI regimen
- Any bypassing or immunomodulatory agents received up to 4 weeks before inhibitor development and any time after
- Withdrawal from the study due to complications assessed as related to inhibitor development
- Any SAE of a bleeding event up to 4 weeks before inhibitor development or any time after
- A pattern of non-serious treated bleeding events which require a change in study drug (rFIXFc) regimen

By definition, all high-titer inhibitors are clinically meaningful, as patients with high-titer inhibitors must either enter the ITI sub-study or withdraw.

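### SAP 9.4.3.3 uses Kaplan-Meier for type-specific inhibitor incidence without saying how other inhibitor types are handled, so those estimates are undefined and can exceed the overall figure

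*SAP*

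**What the plan says.** Under Time to Inhibitor Development (SAP 9.4.3.3, Supporting Analyses) the estimator is named outright: "The cumulative incidence of inhibitors over time (EDs) will be estimated using the Kaplan-Meier method". The figure is split by type: "This will be presented graphically for high and low titer (CS and NCS) inhibitors and overall", subject to the condition "if at least 5 patients develop positive inhibitor". A summary table with the same split follows, and of it the SAP says: "This will include Kaplan-Meier estimates of cumulative incidence of inhibitor development at 10, 20 and 50 EDs". The five-patient condition is attached to the figure only.

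The section has one censoring rule: "For patients who do not have an inhibitor, follow-up time will be censored at the last ED at the time of analysis". It says nothing about a patient who has an inhibitor of a different type from the one being plotted.

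The types come from SAP 5.2.4 and 5.2.5. Section 5.2.4 separates high from low titer and settles discordant results by two of three tests. Section 5.2.5 then says "Within this subgroup, there are several further classifications" and lists three: high titer, low titer that is clinically meaningful, and low titer that is not. I take CS and NCS in 9.4.3.3 to be the last two.

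**The concern.** A patient is placed in one class, so developing one type of inhibitor removes him from the group who could have that type's rivals as their inhibitor. That is a competing-risks setting. One minus Kaplan-Meier for a single type equals the cumulative incidence of that type only if the other types are handled suitably, and the SAP neither states the handling nor names a competing-risks estimator.

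Two programmers could therefore follow 9.4.3.3 faithfully and print different type-specific figures. Under the more common convention, the table could show type rows that add to more than the overall row. It could also show a high-titer figure above the simple proportion that 9.4.3.2 gives for the same patients. High titer is the class that readers will look at first.

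**Working it through.** **Inputs.** N = 30 is the approximate planned enrollment (SAP 3.3). The documents give no expected inhibitor rate and no cumulative-incidence figure, so there is no plan figure to reproduce. All event counts and timings below are assumptions.

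**Conventions compared, at 50 EDs.**
- A: type-specific 1 − KM, with other-type patients censored at inhibitor onset.
- B: type-specific 1 − KM, with other-type patients kept at risk to their last ED.
- C: Aalen-Johansen cumulative incidence, with other types as competing events.

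**Simplest case.** If *l* other-type cases precede *h* cases of the type of interest among *n* at risk, with no other censoring, A gives h/(n − l) and C gives h/n:
- n = 30, l = 3, h = 2: 2/27 = 7.4% against 2/30 = 6.7%.
- n = 20, l = 4, h = 2: 2/16 = 12.5% against 2/20 = 10.0%.
- n = 30, l = 2, h = 1: 1/28 = 3.6% against 1/30 = 3.3%.

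Placing every other-type case first is the ordering that inflates the later type most.

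**Mixed ordering.** Assume 5 inhibitors in 30: low NCS at ED 6, high at 9, low CS at 12, low NCS at 16, high at 22, and nobody else censored before 50 EDs. The overall estimate is 5/30 = 16.67%.

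| Type | A | B | C |
|---|---|---|---|
| High | 1 − (28/29)(25/26) = 7.16% | 2/30 = 6.67% | 6.67% |
| Low CS | 1/28 = 3.57% | 1/30 = 3.33% | 3.33% |
| Low NCS | 1 − (29/30)(26/27) = 6.91% | 2/30 = 6.67% | 6.67% |
| Sum (unrounded) | 17.65% | 16.67% | 16.67% |

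**Early withdrawal under B.** In the same example, suppose the high-titer patient with onset at ED 9 leaves before ED 12. Low CS becomes 1/29 = 3.45% and low NCS becomes 1 − (29/30)(27/28) = 6.79%. High stays at 6.67%. The sum is 16.90% against 16.67%, so part of the excess is back.

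**Other event counts (sum of types against overall).**

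| Scenario | Overall | A | B | C |
|---|---|---|---|---|
| 1 event, no other censoring | 3.33% | 3.33% | 3.33% | 3.33% |
| 3 events, no other censoring | 10.00% | 10.35% | 10.00% | 10.00% |
| 5 events, 5 others censored before 50 EDs | 17.52% | 18.60% | 17.50% | 17.52% |
| 9 events, no other censoring | 30.00% | 33.63% | 30.00% | 30.00% |
| 9 events, 5 others censored before 50 EDs | 31.82% | 35.96% | 31.70% | 31.82% |

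**Simulation.** This used 4,000 trials of 30 patients, types equally likely, events between EDs 4 and 30, and one third of patients with a censoring time before 50 EDs. The mean excess of the sum under A was 0.08, 0.34, 0.98 and 3.48 percentage points at overall risks of 5%, 10%, 16.7% and 30%. Under B the mean gap was below 0.01 point.

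**Scale.** The exact 95% interval for 5/30 runs from 5.6% to 34.7%.

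**The case against.** The strongest reply is that nothing in the SAP requires censoring at onset. Low-titer patients stay on rFIXFc (Protocol 10.2.6.2) and ITI itself uses rFIXFc (Protocol 10.2.6.5), so EDs can keep accruing after an inhibitor. Carry the last-ED rule over to other-type patients and the type estimates almost match the overall. This stands, and it rules out saying that the planned estimator necessarily overstates. It does not supply a rule, though: the last-ED sentence is confined to patients without any inhibitor. Nor does that handling work evenly, because SAP 5.2.5 describes high-titer cases as clinically meaningful "as patients with high-titer inhibitors must either enter the ITI sub-study or withdraw". For those who withdraw, the last ED lies close to onset. The result would then depend on how patients are managed after the inhibitor.

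A reader might also infer that the trial's reported high-titer rate will be biased. The documents do not support that. SAP 9.4.3.2 reports each type as a simple proportion of the Safety Analysis Set; those proportions share a denominator and add up. The overall Kaplan-Meier curve and the primary proportion with its Clopper-Pearson interval are untouched.

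Even with censoring at onset, there is no excess with no inhibitors, with one, or with only one type, and a type whose cases all come first is not inflated. The missing five-patient threshold on the table matters little, since the excess shrinks with few events: 0.35 point at 3 of 30.

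**Conclusion.** The point holds as a gap in specification with a conditional bias. Section 9.4.3.3 names Kaplan-Meier for outcomes that exclude one another and leaves the treatment of other types open. Under censoring at onset, the excess in the sum is about 1 percentage point at 5 inhibitors in 30 (17.65 − 16.67 = 0.98) and about 3.6 to 4.1 points at 9. For high titer alone in the five-inhibitor example it is about half a point (7.16% against 6.67%). All of this is small beside the exact interval for 5/30, and the analysis is descriptive and supporting.

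The conclusion rests on one class per patient and on assumed event counts and timings. The first of these is not fully secured: SAP 5.2.4 settles discordant initial and confirmatory titers, but does not say how a confirmed low-titer inhibitor that later becomes high titer is classed.

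**What to change.** In SAP 9.4.3.3, specify the Aalen-Johansen cumulative incidence function for the type-specific curves and the 10, 20 and 50 ED estimates, with the other inhibitor types as competing events. Count each patient once, under his final class, at the date of the first positive sample that was later confirmed (the inhibitor date in SAP 5.2.4). Keep Kaplan-Meier for the overall curve; the type estimates will then sum to it exactly.

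The cost is a short change of text and a different estimator option in the programming. No new data are needed and the primary analysis does not change. The one small downside is an extra sentence stating how a low-titer inhibitor that later becomes high titer is classed, since the competing-risks estimate depends on it.

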### **9.4.3.4. Additional Analyses**

Patients with low titer inhibitors who remain in the main study may achieve remission without ITI. This is defined as negative inhibitor titers (<0.60 BU/mL) in 2 consecutive determinations 2 – 4 weeks apart. These patients will be listed separately.

### **9.4.4. Incidence of Anti-FIX Antibodies**

The development of anti-rFIXFc [REDACTED] antibodies will be assessed as the number and percentage of patients negative throughout the study, positive at any time following treatment with rFIXFc, and positive at the final evaluation. Percentages will be based on the number of patients who are antibody negative prior to treatment with rFIXFc and have at least one post baseline antibody evaluation for the referenced time point or time interval.

Results from blood samples collected during surgical/rehabilitation periods for the purpose of determining the presence of anti-rFIXFc [REDACTED] antibodies will be included in this analysis.

In addition to a listing of all anti-rFIXFc [REDACTED] antibody results, a separate listing of all results from patients with at least one positive outcome during the study, including at baseline, will be provided.

## **9.5. Vital Signs**

Vital signs include temperature, pulse, systolic and diastolic blood pressure, respiratory rate, height and weight. All vital signs except height and weight were measured prior to and approximately 20 minutes after each dose of rFIXFc. Height and weight were measured prior to dosing. Temperature was measured using the following methods: oral, rectal, tympanic, forehead, and axillary.

Vital signs will be summarized for the observed values and change from baseline using descriptive statistics for the Safety Analysis Set. Post-baseline temperature measurements taken by a method different from baseline will be excluded from the analysis with the exception of the combination of tympanic and rectal measurements. Evaluations taken during major surgical/rehabilitation periods will not be included in any summary.

	Statistical Analysis Plan	Final v1.0
---	----------------------------------	-------------------

A listing of all vital signs will be provided, including from unscheduled visits and during surgical/rehabilitation periods. Vital signs collected during surgical/rehabilitation periods as well as those occurring on the day of surgery will be flagged in this listing.

**9.6. Physical Examination Findings**

All physical examination abnormalities with body system will be listed by patient and visit.

	Statistical Analysis Plan	Final v1.0
---	----------------------------------	-------------------

## 10. CHANGES TO PLANNED ANALYSIS

This SAP is based on Version 3 of the approved study protocol dated 06 August 2018. The major differences in the analysis described in this SAP compared to the protocol are:

- The Full Analysis Set consists of all patients who received at least 1 dose of rFIXFc and were enrolled.
- The protocol mentioned selected analyses may be performed based on a Supporting Analysis Set as appropriate. This analysis set is not defined in the SAP, and all analyses will be based on the analysis populations defined in Section 4.
- The health outcomes questionnaire used in the study is not as specified in the protocol. The analysis described refers to that which was actually used and this can be found in [Appendix A](#).

	Statistical Analysis Plan	Final v1.0
---	----------------------------------	-------------------

## 12. LIST OF TABLES, LISTINGS, AND FIGURES

### List of tables

Background/Demography
Summary of disposition by treatment regimen
Summary of enrollment by country and site by treatment regimen
Summary of patients attending key study visits
Summary of patients attending key ITI study visits
Summary of demographics and baseline characteristics by treatment regimen
Summary of medical and surgical history by treatment regimen
Summary of hemophilia history by treatment regimen
Summary of bleeding history in the 3 months prior to study entry by treatment regimen
Summary of risk factors by inhibitor subgroup
Summary of physical examination at screening by treatment regimen
Summary of prior medications and procedures by treatment regimen
Summary of concomitant medications and procedures by treatment regimen
Summary of major protocol deviations by treatment regimen
Exposure/Dosing
Summary of injections and days of exposure to rFIXFc by treatment regimen
Summary of injections and days of exposure to rFIXFc by EPD entry compliance by treatment regimen
Summary of duration of dosing with rFIXFc by treatment regimen
Summary of duration of dosing with rFIXFc by EPD entry compliance by treatment regimen
Summary of prophylactic dose IU/kg
Summary of ITI dose IU/kg
Summary of prophylactic dosing interval
Summary of ITI dosing interval
Summary of annualized rFIXFc consumption (IU/kg) by treatment regimen
Summary of last prescribed prophylactic dose and dosing frequency
Summary of compliance for the treatment of bleeding episodes by treatment regimen
Summary of prophylactic and ITI dose compliance
Summary of prophylactic and ITI dosing interval compliance
Summary of prophylactic and ITI compliance
Summary of EPD entry compliance by treatment regimen
Efficacy
Summary of bleeding episodes by treatment regimen
Summary of annualized bleeding rates by treatment regimen
Summary of annualized bleeding rate by type of bleed and treatment regimen
Summary of annualized bleeding rate by location of bleed and treatment regimen
Summary of annualized bleeding rate by location, type of bleed and treatment regimen
Summary of annualized bleeding rate by history of bleeding (estimated frequency of bleeds in prior 3 months) by treatment regimen

	Statistical Analysis Plan	Final v1.0
---	----------------------------------	-------------------

Summary of annualized bleeding rate - patients with no major protocol deviations potentially impacting efficacy by treatment regimen
Summary of patient's assessment of response to rFIXFc injections for the treatment of bleeding episodes by treatment regimen
Summary of patient's assessment of response to rFIXFc injections for the treatment of bleeding episodes by compliance to treat the bleed and treatment regimen
Summary of number of injections required for resolution of a bleeding episode by treatment regimen
Summary of dose (IU/kg) of rFIXFc for resolution of bleeds by treatment regimen
Summary of physician's global assessment of the response for episodic and prophylactic regimens
Summary of physician's global assessment of the response for ITI regimens
Summary of health outcomes for episodic and prophylactic regimens
Summary of incremental recovery (IR) (IU/dL per IU/kg) for episodic and prophylactic regimens
ITI
Summary of ITI response
Surgery
Investigators'/surgeons' assessment of patients' hemostatic response to rFIXFc post major surgery
Number of injections and dose required to maintain hemostasis during major surgery
Estimated total blood loss during major surgery
Total rFIXFc consumption (IU/kg) per major surgery
Summary of number of bleeds after surgery per major surgery
Adverse events
Overall summary of rFIXFc treatment-emergent adverse events by treatment regimen
Overall summary of rFIXFc treatment-emergent adverse events by treatment regimen and EPD entry compliance
Summary of rFIXFc treatment-emergent adverse events by treatment regimen
Summary of rFIXFc treatment-emergent adverse events by treatment regimen and EPD entry compliance
Summary of rFIXFc treatment-emergent adverse events by treatment regimen and preferred term in descending order of incidence
Summary of rFIXFc treatment-emergent serious adverse events by treatment regimen
Summary of rFIXFc treatment-emergent adverse events by severity and treatment regimen
Summary of rFIXFc treatment-emergent adverse events by relationship to treatment and treatment regimen
Summary of severe rFIXFc treatment-emergent adverse events by treatment regimen and preferred term in descending order of incidence
Summary of rFIXFc treatment-emergent adverse events leading to treatment discontinuation and/or study withdrawal by treatment regimen
Routine laboratory
Summary of laboratory results and change from baseline for episodic and prophylactic

	Statistical Analysis Plan	Final v1.0
---	----------------------------------	-------------------

regimens: Hematology
Summary of laboratory results and change from baseline for ITI regimen: Hematology
Shifts from baseline to minimum/maximum post-baseline value for laboratory results: Hematology
Summary of shifts from baseline to minimum/maximum post-baseline value for laboratory results: Hematology
Summary of potentially clinically significant laboratory abnormalities: Hematology
Summary of laboratory results and change from baseline for episodic and prophylactic regimens: Blood Chemistry
Summary of laboratory results and change from baseline for ITI regimen: Blood Chemistry
Shifts from baseline to minimum/maximum post-baseline value for laboratory results: Blood Chemistry
Summary of shifts from baseline to minimum/maximum post-baseline value for laboratory results: Blood Chemistry
Summary of potentially clinically significant laboratory abnormalities: Blood Chemistry
Inhibitors
Summary of inhibitor development by Nijmegen-modified Bethesda assay
Summary of time to inhibitor development
Other Safety
Summary of anti-rFIXFc antibodies
Summary of vital sign results and change from baseline for episodic and prophylactic regimens
Summary of vital sign results and change from baseline for ITI regimen

**List of listings**

Background/demography
Listing of lot numbers for study drug
Listing of protocol versions consented to
Listing of end of study disposition
Listing of demographic and baseline characteristics
Listing of caregiver’s demography
Listing of medical and surgical history
Listing of informed consent date and analysis populations
Listing of hemophilia history – diagnosis and diagnostic factors
Listing of Hemophilia history – bleeding history 3 months prior to screening
Listing of risk factors
Listing of prior and concomitant medication taken through the end of study visit
Listing of concomitant medication taken after the end of study visit and prior to follow-up
Listing of maternal concomitant medication taken through the end of study visit
Listing of maternal concomitant medication taken afer the end of study visit and prior to follow-up
Listing of other therapy or concomitant procedures

	Statistical Analysis Plan	Final v1.0
---	----------------------------------	-------------------

Listing of major and minor protocol deviations
Exposure/dosing
Listing of all injections and treated bleeding episodes
Listing of injections to treat a bleed
Listing of exposure
Listing of dose and consumption endpoints
Listing of prescribed dose and regimen changes
Listing of compliance endpoints
Efficacy
Listing of the number of bleeding episodes during the efficacy period
Listing of derived bleeding endpoints based on individual bleeding episodes
Listing of derived bleeding and injection endpoints based on patients
Listing of the Investigator’s classification of bleeding episodes which differed from the caregiver’s classification
Listing of the by-patient summary of the assessment of response to rFIXFc for the treatment of bleeding episodes
Listing of physician’s global assessment of the patient’s response to his treatment regimen
Listing of health outcomes
Listing of FIX activity levels
Listing of incremental recovery
ITI
Listing of patients on ITI
Surgery
Listing of major surgery information – hospitalization data
Listing of major surgery information – blood loss
Listing of major surgery information – dosing during and for the first 14 days post surgery
Listing of major surgery information – transfusions and surgeon’s assessment of hemostatic response to rFIXFc
Listing of injections and bleeding episodes during and for the first 14 days following major surgery
Listing of minor surgery information – hospitalization data
Listing of minor surgery information – blood loss
Listing of minor surgery information – dosing during and on the day of surgery
Listing of minor surgery information – transfusions and surgeon’s assessment of hemostatic response to rFIXFc
Adverse events
Listing of adverse events
Listing of serious adverse events
Listing of related adverse events
Listing of adverse events leading to treatment discontinuation and/or study withdrawal
Listing of adverse events during major surgical/rehabilitation periods
Listing of deaths

	Statistical Analysis Plan	Final v1.0
---	----------------------------------	-------------------

Routine laboratory
Listing of laboratory normal ranges
Listing of laboratory values: Hematology
Listing of abnormal laboratory values based on the normal range: Hematology
Listing of abnormal laboratory values based on potentially clinically significant abnormalities: Hematology
Listing of laboratory values: Blood Chemistry
Listing of abnormal laboratory values based on the normal range: Blood Chemistry
Listing of abnormal laboratory values based potentially clinically significant abnormalities: Blood Chemistry
Inhibitors
Listing of laboratory values: Inhibitor results
Listing of abnormal laboratory values: Inhibitor results
Listing of inhibitor patients who achieve remission without ITI
Listing of inhibitor patients
Other safety
Listing of laboratory values: Anti-rFIXFc antibodies
Listing of abnormal laboratory values: Anti-rFIXFc antibodies
Listing of vital sign measurements
Listing of abnormal findings from physical examination
Listing of weight

